# Pharmacokinetic Assessments:

Pharmacokinetic blood samples (approximately 10 mL per sample) will be collected for determination of avobenzone, oxybenzone, octocrylene, ecamsule, homosalate, octisalate and octinoxate plasma concentrations, where applicable to the different sunscreen formulations, at the following time points:

- Day 1: 0 and 0.5, 1, 1.5, 2, 3 (Part 2 only), 4, 6, 8, 9, 10, 12, and 14 hours after initial dose
- Day 2: 23, 28, 33 h
- Day 3: 47, 52, 57 h
- Day 4: 71, 73, 74, 76, 78, 81, 82, 84 and 86 h
- Day 5: 95 hours
- Day 6: 120 hours
- Day 7: 144 hours
- Day 10: 216 hours (Part 2 only)
- Day 14: 312 hours (Part 2 only)
- Day 21: 480 hours (Part 2 only)

NOTE: when a time point corresponds with sunscreen administration, the PK sample will be collected before sunscreen administration.

The following PK parameters will be determined for each subject for each sunscreen active ingredient:

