Part 2 is an open-label, 4-arm study to evaluate the pharmacokinetics of avobenzone, oxybenzone, octocrylene, homosalate, octisalate and octinoxate (where applicable [Part 2 products will not contain ecamsule]) after multiple applications of a topical sunscreen formulation in healthy adult subjects. Part 2 will include 48 subjects (24 male and 24 female) and each arm will include 12 subjects (6 male and 6 female). One of the formulations in Part 2 will be selected based on the plasma exposure data from the pilot study (Part 1) along with 3 additional formulations. A total of 48 subjects (24 male and 24 female) will be admitted to the CRU on Day 0. On the morning of Days 1 through 4, subjects will receive a topical application of the study product at approximately 0900 hours. The study drug will be weighed in advance and applied by a qualified person from the study team. Subjects will only receive one application on Day 1. On Days 2, 3 and 4, subjects will receive an initial dose and 3 more topical applications on the same day at 2, 4, and 6 hours after the first dose.

### Parts 1 and 2

In both parts, approximately 2 mg of active sunscreen ingredient per 1 cm^2 of body surface (calculation per method of Dubois) will be evenly applied 4 times per study day (except for a one-time application on the first day in part 2) to areas of the body typically exposed to the sun: face, ears, neck, torso, arms, and legs (approximately 75% of the body surface area). The antecubital areas will be avoided when applying the sunscreen due to potential contamination of the sites used for intravenous PK blood sample collection. The topical applications of study drug will be administered with subjects in swim wear to simulate real-world settings as well as for easy application. In addition to swim wear, subjects may wear scrubs in between applications and at other times throughout the day/night. Subjects are required to shower each morning after the first PK blood sample collection (and before the first dose of the day), but not at other times during the day.

Blood samples (approximately 10 mL per sample) will be collected for determination of plasma concentrations for all active ingredients (avobenzone, oxybenzone, octocrylene, ecamsule, homosalate, octisalate and octinoxate, where applicable).

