# 5. Investigational Plan

# 5.1. Study Design

This will be a single clinical study conducted in 2 parts. The duration of study participation will be approximately 37 days for part 1, including a 30-day screening period, a 4-day treatment period (Days 1-4) and subjects leaving the clinic on the morning of Day 7 following completion of scheduled End-of-Study activities. For part 2, the duration of participation will be approximately 51 days, including a 30-day screening period, a 4-day treatment period (Days 1-4) and subjects leaving the clinic on the morning of Day 7. Subjects in part 2 will then return to the clinical for follow-up visits on Days 10, 14 and 21 after which End-of-Study activities will be completed.

#### 5.1.1 Part 1

Part 1 is an open-label, randomized, 4-arm pilot study to evaluate the effects of multiple applications of 4 different topical sunscreen formulations in healthy adult subjects. Each arm will include 6 subjects (3 male and 3 female) with 1 formulation. A total of 24 subjects (12 male and 12 female) from all 4 arms will be admitted to the clinical research unit (CRU) on Day 0.

On the morning of Days 1 through 4, subjects will receive a topical application of the study product at approximately 0900 hours. The study drug will be weighed in advance and applied by a qualified person from the study team. Subjects will then receive 3 more topical applications on the same day at 2, 4, and 6 hours after the first dose.

### 5.1.2 Part 2

Part 2 is an open-label, 4-arm-study to evaluate the pharmacokinetics of avobenzone, oxybenzone, octocrylene, homosalate, octisalate and octinoxate (Part 2 products will not contain ecamsule) after multiple applications of a topical sunscreen formulation in healthy adult subjects. Part 2 will include 48 subjects (24 male and 24 female) and 12 subjects in each arm (6 male and 6 female). One of the formulations in Part 2 will be selected based on the plasma exposure data from the pilot study (Part 1). In addition, 3 new formulations will be added.

On the morning of Days 1 through 4, subjects will receive a topical application of the study product at approximately 0900 hours. The study drug will be weighed in advance and applied by a qualified person from the study team. Subjects will only receive one application on Day 1. On Days 2, 3 and 4, subjects will receive an initial dose and 3 more topical applications on the same day at 2, 4, and 6 hours after the first dose.

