### Across all study days (Primary Endpoint)

• Maximum concentration (observed peak drug concentration) (Cmax)

#### Days 1

- Maximum concentration (observed peak drug concentration) (Cmax)
- Time at which  $C_{max}$  occurs  $(T_{max})$

• AUC from time 0 to the sampling time corresponding to the last quantifiable concentration (Clast) (AUC0-t), calculated by the mixed linear logarithmic trapezoidal method

### Days 2 and 3

- Residual drug concentration (predose level) (Ctrough)
- 3 h post dose concentration

### Day 4

- Elimination rate constant (Kel), obtained by linear regression of the log-linear terminal phase of the concentration-time profile using at least 3 data points, excluding Cmax, otherwise Kel will not be determined. The acceptability criteria for determination of Kel will be a coefficient of regression more than or equal to 0.98.
   When Kel will not be determined, AUC0-inf and t1/2 will not be reported.
- Terminal half-life  $(t_{1/2})$ , calculated using the equation  $\ln 2/k$  after the last study drug application (on Day 4)
- Accumulation ratios, calculated using the following formula:

$$R_1 = AUC_{0-23} Day 4 / AUC_{0-23} Day 1$$

• AUC from time 0 extrapolated to infinity (AUC0-inf), calculated by the mixed linear-logarithmic trapezoidal method as:

$$AUC_{0\text{-inf}} = AUC_{0\text{-t}} + C_{last} / K_{el}$$

When the extrapolation represents more than 20%,  $AUC_{0-inf}$  and  $t_{1/2}$  will not be reported.

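### On Days 2 to 4 of Part 2 no blood is drawn in the 3 h after the fourth application, so the observed Cmax can miss an early peak at the heaviest load; the size is conditional and the remedy cheap

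*Protocol*

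**What the plan says.** Protocol 5.1.2 starts each treatment day at about 0900. For Part 2 it states "Subjects will only receive one application on Day 1", and on Days 2, 3 and 4 "an initial dose and 3 more topical applications on the same day at 2, 4, and 6 hours after the first dose".

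The sampling list is the same in the synopsis, protocol 5.7.1.1, the footnote to Table 10-1 and SAP Attachment A. Day 2 has draws at 23, 28 and 33 h, Day 3 at 47, 52 and 57 h, and Day 4 is given as "Day 4: 71, 73, 74, 76, 78, 81, 82, 84 and 86 h". The first day is sampled densely: "Day 1: 0 and 0.5, 1, 1.5, 2, 3 (Part 2 only), 4, 6, 8, 9, 10, 12, and 14 hours after initial dose". A note adds that "when a time point corresponds with sunscreen administration, the PK sample will be collected before sunscreen administration".

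Protocol 5.7.1.4 makes Cmax across all study days the primary endpoint. SAP section 5 names avobenzone Cmax as the primary outcome, defines it as the observed maximum, and specifies non-compartmental analysis.

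**The concern.** The trial is meant to capture exposure under maximal use. In Part 2 the cumulative load is greatest just after the last of 13 applications, at 78 h, and the next 3 h are unsampled. Days 2 and 3 leave the same interval open. A non-compartmental observed maximum cannot recover a peak that was not drawn, and the Day 4 Tmax listed in the synopsis and SAP cannot fall strictly between 78 and 81 h.

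The design does allow for an early peak: it draws at 0.5, 1, 1.5, 2 and 3 h after the first application. In Part 2 that dense sampling follows a single application only. Part 1 has an 8 h draw on Day 1, 2 h after a fourth application, but on the four-application days of Part 2 no draw plays that role.

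Any resulting error in Cmax is downward. Its size would depend on absorption speed, so it could differ between the lotion, the two kinds of spray and the oil.

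**Working it through.** **Timing.** With first doses at 0, 24, 48 and 72 h and further applications 2, 4 and 6 h later, the fourth applications of Part 2 fall at 24 + 6 = 30 h, 48 + 6 = 54 h and 72 + 6 = 78 h. SAP section 5 describes the late sample on Days 2 and 3 as 3 h after the day's last dose, which is reproduced: 33 − 30 = 3 h and 57 − 54 = 3 h. On Day 4, 81 − 78 = 3 h. With the ±5 min window in protocol 5.7.1.1, the earliest possible draw is 2 h 55 min after the application.

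For the other Day 4 applications:

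- First (72 h): draws 1 h and 2 h later, at 73 and 74 h.
- Second (74 h): draw 2 h later, at 76 h.
- Third (76 h): draw 2 h later, at 78 h.

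**Size.** The kinetics below are assumptions, not figures from the documents. Take a one-compartment model with first-order input and no assay noise, summed over the 13 Part 2 applications (0; 24, 26, 28, 30; 48, 50, 52, 54; 72, 74, 76, 78 h):

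C(t) = Σ ka/(ka − ke) × [exp(−ke·u) − exp(−ka·u)], where u is the time since each application already made.

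Here ke = ln 2 / half-life, and ka is solved from ln(ka/ke)/(ka − ke) = the single-application peak time. Loss = 1 − (largest C at a scheduled draw)/(largest C on a 0.01 h grid).

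Example: peak 2 h, half-life 24 h. ke = 0.693/24 = 0.0289 and ka = 2.194; check: ln(2.194/0.0289)/(2.194 − 0.0289) = 4.33/2.165 = 2.0 h. The true maximum is at 79.14 h and the highest scheduled draw is at 81 h, with ratio 0.960, a loss of 4%.

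Percentage loss in Cmax, current schedule → 82 h moved to 80 h:

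| Single-application peak | Half-life 3 h | 6 h | 12 h | 24 h | 48 h |
|---|---|---|---|---|---|
| 1 h | 28 → 20 | 21 → 11 | 12 → 6 | 6 → 3 | 3 → 2 |
| 2 h | 18 → 7 | 13 → 4 | 7 → 2 | 4 → 1 | 2 → 1 |
| 3 h | 8.6 → 1.2 | 5.9 → 0.7 | 3.7 → 0.4 | 2.2 → 0.3 | 1.2 → 0.1 |
| 4 h | 2.1 → 0.0 | 1.8 → 0.0 | 1.4 → 0.0 | 0.9 → 0.0 | 0.5 → 0.0 |
| 8 h | 0.0 → 1.0 | 0.1 → 1.6 | 0.0 → 1.0 | 0.0 → 0.5 | 0.0 → 0.5 |

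At 5 and 6 h both schedules lose at most about 0.3%; at 10 h both lose 0.2 to 0.4%.

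Two features matter. Because doses overlap, a single-application peak at 3 h puts the true maximum near 79.5 h, inside the gap. With a peak at 8 h the maximum lies near 82 h, at the draw that would be moved, so there the swap does slight harm.

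**The case against.** - **No kinetics are given.** This stands. The largest losses need a peak at 2 h or earlier together with a short half-life. Part 2 also follows plasma to 480 h and strips skin on Days 7 and 14 to look for a deposit. That does not establish slow kinetics, but it makes the longer half-lives more relevant. At 24 to 48 h the loss is 3 to 6% for a 1 h peak and 2 to 4% for a 2 h peak, and the swap recovers about 1 to 3 percentage points.
- **Day 4 does have early draws.** This stands too. Only the last application lacks a draw within 2 h. Those draws come at lower loading, and the model already credits them, so they limit the loss without removing it.
- **Part 2 Day 1 shows each product's single-application Tmax.** It does, so an early peak could be recognised afterwards. The reported Cmax would still be the uncorrected observed maximum.
- **The analysis is descriptive and exploratory.** Correct, and it lowers the priority. Every discrete schedule understates the true maximum somewhat.

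A reader might infer that Cmax will be understated by some 18 to 28%, or that product comparisons will be biased. The documents support neither: they give no absorption rate, and they specify no between-product test of Cmax. Nor is it right that the swap is neutral for all peaks at 6 h or later, as the 8 h row shows.

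**Conclusion.** The gap is a matter of arithmetic under the explicit application times: 30 to 33, 54 to 57 and 78 to 81 h are unsampled. That the observed Cmax can miss a peak there follows directly. Whether it will, and by how much, rests on assumed kinetics: the loss runs from almost nothing for peaks at 5 h or later to 28% for a 1 h peak with a 3 h half-life, always downward.

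The timing also depends on an unresolved inconsistency. The synopsis entry on study drug and dosage says the four daily Part 2 applications extend over eight hours, which does not match the 2, 4 and 6 h times elsewhere. If the fourth application came at 8 h, on Day 4 it would fall at 80 h, and the existing 81 and 82 h draws would be 1 h and 2 h after it.

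This is a low-priority improvement to a descriptive endpoint, worth making because it costs almost nothing.

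**What to change.** 1. Reconcile the eight-hour statement in the synopsis with the 2, 4 and 6 h application times before changing any draw. If the last application is at 8 h, do not make the swap: an 80 h draw would be pre-application under the coincidence note, and the draw 2 h after the application would be lost.
2. If the explicit times stand, move the Day 4 draw at 82 h to 80 h in the synopsis, protocol 5.7.1.1, the Table 10-1 footnote and SAP Attachment A. Keep 81 h, which matches the 3 h post-dose draws at 33 and 57 h. Day 4 becomes 71, 73, 74, 76, 78, 80, 81, 84 and 86 h.

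The number of draws and the blood volume are unchanged. The 80 h draw then mirrors the Day 1 draw at 8 h.

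There are two costs. The Day 1 draw at 10 h loses its Day 4 counterpart, in a stretch still bracketed by 81 and 84 h. For products peaking near 8 h, Cmax loses about 0.5 to 1.6%. Against that, the largest gain is about 11 percentage points (18 → 7, peak 2 h, half-life 3 h). Very early peaks are only partly covered: a 1 h peak with a 3 h half-life still loses 20%.

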### Across all study days

• Maximum concentration (observed peak drug concentration) (Cmax)

#### Day 1

- Maximum concentration (observed peak drug concentration) (Cmax)
- Time at which  $C_{max}$  occurs  $(T_{max})$
- AUC from time 0 to the sampling time corresponding to the last quantifiable concentration (Clast) (AUC0-t)

#### Days 2 and 3

- Residual drug concentration (predose level) (Ctrough)
- 3 h post dose concentration

#### Day 4

- Maximum concentration (observed peak drug concentration) (Cmax)
- Time at which  $C_{max}$  occurs  $(T_{max})$
- Elimination rate constant (Kel)
- Terminal half-life  $(t_{1/2})$

	• AUC from time 0 to the sampling time corresponding to the last quantifiable concentration (C last ) (AUC 0-t )
	• AUC from time 0 extrapolated to infinity (AUC 0-inf )
	Day 5, 6, 7, 10 (Part 2 only), 14 (Part 2 only) and 21 (Part 2 only)
	Residual drug concentration (C trough )
	Tape Stripping to Determine Residual Skin Concentration
	In addition, skin tape stripping of the lower back (around 3.8 cm  area) will be conducted once on Days 7 and 14 in part 2 to determine residual sunscreen active ingredients in the superficial layers of the skin.
Safety Assessments:	Safety will be evaluated in terms of AEs, vital sign measurements (blood pressure, heart rate, respiratory rate, and oral body temperature), and physical examination findings.
Sample Size:	Approximately 72 healthy subjects are planned for enrollment, of which 24 subjects will be enrolled and randomized in Part 1 and 48 subjects will be enrolled and randomized in Part 2. The sample size was determined empirically and is typical for exploratory investigations of this type.
Statistical Methods:	All data will be presented in data listings. Data from subjects excluded from an analysis population will be presented in the data listings but not included in the calculation of summary statistics. The number of subjects who enroll in the study and the number and percentage of subjects who complete each assessment will be presented. The frequency and percentage of subjects who withdraw or discontinue from the study and the reason for withdrawal or discontinuation will be summarized. Demographic and baseline characteristics will be summarized overall and by treatment for all subjects.
	Descriptive statistics will be used to summarize demographic and baseline subject characteristics. For continuous variables, the mean, median, standard deviation (SD), minimum, and maximum values will be reported. For categorical (nominal) variables, the number and percentage of subjects (or observations) will be reported.
	Pharmacokinetics: The PK population will include all subjects who receive study drug and have at least 1 estimable PK parameter after dosing. Plasma concentrations and PK parameters of avobenzone, oxybenzone, octocrylene, ecamsule, homosalate, octisalate and octinoxate, where applicable, will be listed and summarized using descriptive statistics (n, arithmetic mean, SD, minimum, median, and maximum) by nominal PK sampling time.
	Safety: The safety population will include all subjects who receive at least 1 dose of any of the study drugs. Any AEs will be coded using the Medical Dictionary for Regulatory Activities (MedDRA). The incidence of AEs, organized by system organ class and preferred

	term, will be summarized with a focus on treatment-emergent AEs. Vital sign measurements will be summarized using descriptive statistics by time point. All values will be evaluated for clinically notable results. Data for additional safety parameters (e.g., physical examination findings) will be listed.
Date of Protocol:	13 December 2018

# 2. List of Abbreviations

Abbreviation	Definition
AE	adverse event
AUC	area under the concentration-time curve
AUC 0-24	area under the concentration-time curve from time 0
$\mathrm{AUC}_{0 ext{-inf}}$	through 24 hours after dosing area under the concentration-time curve from time 0 extrapolated to infinity
$\mathrm{AUC}_{0 ext{-t}}$	area under the concentration-time curve from time 0 to the sampling time corresponding to the last quantifiable concentration
CFR	Code of Federal Regulations
$C_{last}$	time corresponding to the last quantifiable concentration
$C_{\text{max}}$	maximum concentration (observed peak drug
CRU	concentration) clinical research unit
Ctrough	residual drug concentration (predose level)
ECG	electrocardiogram
eCRF	electronic case report form
FDA	Food and Drug Administration
GCP	Good Clinical Practice
HIPAA	Health Insurance Portability and Accountability Act
HIV	human immunodeficiency virus
IAA	IRB Authorization Agreement
ICH	International Council for Harmonisation
IRB	institutional review board
IV	intravenous
$K_{el}$	elimination rate constant
MedDRA	Medical Dictionary for Regulatory Activities
MUsT	Maximum Usage Trial
OTC	over the counter
PK	pharmacokinetic
SAE	serious adverse event
SD	standard deviation
$t_{1/2}$	terminal half-life
TEAE	treatment-emergent adverse event
$T_{\text{max}}$	time at which C max occurs
UV	ultraviolet
U.S.	United States

### 3. Introduction

Sunscreens prevent skin damage by reflecting or absorbing ultraviolet (UV) radiation and they are regulated as drug products in the United States (U.S.). Most active ingredients in sunscreens are organic chemicals and some have been shown to be absorbed through human skin with detectable levels in the blood or urine. As part of the safety evaluation for sunscreen products, the Food and Drug Administration (FDA) requests an assessment of systemic absorption in humans so that human blood levels can be compared with exposure levels obtained in nonclinical toxicology studies. If testing establishes that the sunscreen is not absorbed through the skin into the body, some aspects of toxicology testing may not be needed.

Sunscreen products may be applied multiple times daily as both primary sunscreen products and as ingredients in cosmetic products, in substantial amounts for a lifetime starting at 6 months of age. The amount of sunscreen ingredient in a product can vary, but permitted levels can be as high as 15% for some organic active ingredients and application to the skin can accumulate to gram quantities in a day even with modest use. Because of the significant use of these sunscreens, even a low percentage of systemic absorption (e.g., 0.1%) could represent a significant systemic exposure in a single day and over a lifetime.

The Surgeon General's Call to Action to Prevent Skin Cancer calls on partners in prevention from various sectors across the nation to address skin cancer as a major public health problem by increasing awareness of skin cancer and promoting actions to reduce its risk. Given the recognized public health benefits of sunscreen use, the FDA is committed to finding ways to facilitate the marketing of sunscreen products that include additional over-the-counter (OTC) sunscreen active ingredients. The FDA will continue to work with industry and other public health agencies to ensure that the sunscreens consumers use are safe and effective for daily, life-long use.

In November 2016, the U.S. FDA finalized the guidance titled "Guidance for Industry: Nonprescription Sunscreen Drug Products Safety and Effectiveness Data" (sunscreen guidance) DHHS, 2016) [1]. The guidance requests an assessment of the human systemic absorption of sunscreen ingredients with a Maximum Usage Trial (MUsT). The FDA sunscreen guidance notes that some nonclinical toxicity studies may be waived if results of an adequately conducted human pharmacokinetic (PK) MUsT shows a steady-state blood level less than 0.5 ng/mL.

Periodically, the FDA performs testing of products and formulations that the Agency sees as important for public health. This testing is not a reflection of rulemaking or other regulatory actions, but instead is done independently to measure the agency's understanding of the products' overall safety and effectiveness.

This study is not intended to meet all requirements of MUsT studies as outlined in the FDA guidance referenced above, but will follow many of the principles.

# 4. Study Objectives

### 4.1. Primary Objectives

### 4.1.1 Part 1

Part 1 is an open-label, randomized, 4-arm study in 24 healthy adult subjects with the primary objective:

• To explore whether the active components (avobenzone, oxybenzone, ecamsule and octocrylene) of 4 sunscreen products (1 sunscreen product in each arm) are absorbed into the systemic circulation when sunscreen is applied under maximal-use conditions.

One sunscreen product with the highest avobenzone exposure will be selected for the second part of the study. If there is no quantifiable exposure of avobenzone for any of the sunscreen products, the formulation with the highest oxybenzone exposure will be selected for Part 2.

### 4.1.2 Part 2

Part 2 is an open-label, 4-arm study in 48 healthy adult subjects with the following primary objective:

• To assess, where applicable, the pharmacokinetics and systemic absorption of the active components (avobenzone, oxybenzone, octocrylene, ecamsule, homosalate, octisalate and octinoxate) of 4 sunscreen products (1 sunscreen product in each arm) under maximal-use conditions.

